2.0 Background

One in 8 women will be diagnosed with breast cancer in their lifetime,¹ and 90% will survive at least five years post diagnosis.² For many BCS, however, Cardiovascular disease (CVD) related deaths are a greater risk to early mortality than cancer recurrence, accounting for 35% of deaths among BCS.³⁻⁵ Some BCS are at risk for CVD development at the time of their initial cancer diagnosis. Many more women however, develop MetS, a cardinal CVD risk factor during or after treatment, in part, as a result of cardiotoxic cancer treatment regimens.⁶⁻⁷ The presence of MetS increases the risk of developing CVD up to five fold,⁸⁻⁹ and includes having three of the following five criteria: (a) a large waistline; (b) elevated blood pressure; (c) elevated HbA1c levels; (d) elevated triglyceride levels; and (e) low HDL cholesterol levels.⁹

Modifying dietary and physical activity behaviors remains the best means of reducing MetS and CVD risk among the general population.¹⁶⁻¹⁸ Only a handful of studies, however, have examined the impact of such changes on MetS among BCS. Those studies, while small, suggest that healthful dietary and physical activity behavior change results in improvements in quality of life and biomarkers of cardiovascular health and reductions in cancer-related physical symptoms (e.g., fatigue, limited mobility),¹⁹⁻²¹ as well as empowering BCS to take control over their risk of cancer recurrence.²² Considering the potential benefits of MetS reduction programming, there is a need to create programs that are accessible to a range of populations.

An additional concern however is that intervention trials in cancer survivors and the general population repeatedly demonstrate that health behavior changes made during interventions are

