3.0 Study Design

Experimental Design and Methods

We will use a 1-arm pre-post design to examine the feasibility and preliminary effect of the intervention compared to enhanced usual care. We will randomize $n = 48$ BCS (ages 18 and older) with MetS, to either the treatment or enhanced usual care condition. All participants will complete baseline and follow-up data collection at weeks 0 and 13 respectively. To track habit formation during the intervention, treatment participants will complete a text message delivered, single item behavioral automaticity measure two weeks apart (week 0-2).

Trial Setting, Sampling, and Recruitment. We will recruit our sample of $n = 48$ BCS in collaboration with the Karmanos Cancer Institute’s Detroit hospital clinic. Trained RAs located at the clinics will screen, consent, and enroll eligible participants following an IRB approved protocol. We will also recruit participants from the Cancer Survivorship in Metropolitan Detroit study (IRB# 120714MP2F). We will submit a data request to obtain the contact information of participants who may meet the criteria for MetS and who have agreed to be contacted in the future about additional research studies (see recruitment below). A trained RA will then call the participant and using an IRB approved script, screen the potential participant for eligibility and provide an overview of the study.

Inclusion Criteria: English speaking, females ages 18 and older with a diagnosis of stage 1-3 histologically confirmed first cancer of the breast will be invited to participate. Three of the following 5 criteria must be present for MetS: a large waistline (> 40 inches for men and > 35 inches for women); systolic blood pressure ≥ 130 ; HbA1c of $\geq 5.7\%$; triglyceride levels > 150 mg/dL; and HDL cholesterol levels < 50 mg/dL. However, since we will be recruiting participants from a variety of setting, and not all sources will have available MetS data, we will use a modified classification criteria, based on recruitment source. Those procedures are described below.

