Clinic-based recruitment. Participant screening and consent will occur as follows: (1) a trained clinic-based RA will screen potential participants first through clinic chart review. Once potential participants are identified, the RA will confirm preliminary inclusion/exclusion with the treating physician; (2) once eligibility is confirmed, the RA will approach the potential participant with an IRB approved recruitment script and notify them of their potential eligibility to participate in the study. If the potential participant is interested, the RA will use the script to provide the participant an overview of the study; (3) if the participant is still interested in participating, the RA will obtain informed written consent in the clinic using an IRB approved consent form. The RA will also tell the potential participant that confirmation of Mets, via blood testing will occur after obtaining informed consent. The RA will also explain to the potential participant that if the confirmatory blood tests do not indicate that the individual has Mets, then they would be automatically disenrolled from the study and notified of the disenrollment. Once consented, the RA will measure the participant's waist, and confirm the participant's blood pressure through measuring the mean of 3 reads on the same arm (for the day of the visit), and ensure the physician orders the lab blood draw and that the participant completes the lab draw so that samples can be sent to the clinical laboratory for analysis of MetS factors. The RA will discuss with the participant that the remaining baseline data collection will occur once MetS status has been confirmed from the blood test and that an RA from WSU will contact the participant to notify them of their eligibility status post-blood draw.

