Cancer Survivorship in Metropolitan Detroit recruitment. We will submit a data request [IRB # 120714MP2F] to obtain the contact information of participants that agreed to be contacted in the future about research studies and who self-reported a history of two of the following four criteria: high cholesterol, hypertension, diabetes, and a BMI of ≥ 25 . Potentially eligible ROCs participants will be contacted by a trained RA and further screened for study eligibility over the phone. Once eligibility is confirmed, the RA will notify them of their potential eligibility to participate in the study. If the potential participant is interested, the RA will make an appointment to go to the participant's home (or the study lab-participant choice) to obtain informed written consent.

Trial Procedures

Upon completion of study consent the RA will make arrangements for baseline data collection within 7-14 days following the informed consent process.

Confirmatory MetS Testing and Baseline Data Collection

Clinic-based participants. After the clinic-based RA confirms the participants MetS status from the blood draw results, the clinic RA will email the participant's MetS data and contact information via secure encrypted email to the study coordinator. The study coordinator will review the MetS data and confirm eligibility. If the participant is still eligible to participate in the study, the coordinator will then schedule a visit to come to the participant's home for the first of two baseline data collection visits. If the participant is no longer eligible to participate after reviewing the MetS data, the coordinator will contact the participant to notify them that they have been disenrolled.

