For eligible participants, the coordinator will next contact the participant and schedule the first of two baseline data collection visits. The first visit be in person and will consist of the participant completing psychosocial measures, a 24 hour dietary recall, and being shown how to use an activity tracking device to track their activity (if asked to complete this component) as well as be shown how to complete the symptom burden tracking (if selected to complete this component). The second visit will be conducted over the phone and consist of the RA completing the online dietary recall with the participant. Seven days after the first visit, and only if the participant was asked to either complete the activity tracking, an RA will visit the participant at their home to pick up the activity tracker.

Cancer Survivorship in Metropolitan Detroit participants. After signing the informed consent the RA will make an appointment to collect baseline data. Data collection, including a blood draw to confirm MetS status will occur in the participant's home. A phlebotomist from the Karmanos Cancer Institute's Epidemiology Research Core (ERC) will travel to the participants home to conduct a blood draw. Results of the blood testing and the participant contact information will be emailed via secure encrypted email to the study coordinator. The study coordinator will review the MetS data and confirm eligibility. If the participant is still eligible to participate in the study, the coordinator will then schedule a visit to come to the participant's home for the first of two baseline data collection visits. If the participant is no longer eligible to participate after reviewing the MetS data, the coordinator will contact the participant to notify them that they have been disenrolled.

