For eligible participants, the coordinator will next contact the participant and schedule the first of two baseline data collection visits. The first visit be in person and will consist of the participant completing psychosocial measures, a 24 hour dietary recall, and being shown how to use an activity tracking device to track their activity (if asked to complete this component) as well as be shown how to complete the symptom burden tracking (if selected to complete this component). The second visit will be conducted over the phone and consist of the RA completing the online dietary recall with the participant. Seven days after the first visit, and only if the participant was asked to either complete the activity tracking, an RA will visit the participant at their home to pick up the activity tracker.

The first intervention visit occurs 2 weeks after the participant completes baseline data collection (including any optional study activities). Participants will participate in the initial coaching session, followed by 11 additional sessions during weeks 2-12. We will schedule all participants for clinic-based follow-up data collection visits at week 13 where we will collect a consistent set of study measures. One exception to the clinic based data collection is the NCI dietary recall measure, which, similar to baseline data collection, will be conducted over the phone with the participant on two non-consecutive days during week 13. Participants will receive

a total of \$100 in compensation paid via pre-paid Visa cards for completing the weeks 0 and 13 study visits. Participants who complete the option data collection are eligible to receive an additional \$25 in compensation for their time and effort. Optional activities include symptom reporting, activity tracking and exit interview.

Treatment Description.

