Objective Physical activity (subsample of participants). We will collect data for baseline objective physical activity using the ActivPal⁷³ wireless activity tracker. The ActivPal is a wireless activity tracker that adheres to the thigh using Tegaderm. Participants will wear an ActivPal device on their thigh for seven days to collect data on total physical activity during their waking hours. The Activpal does not require any effort on the part of the participant once it is adhered. The RA will remove the tracker after a 7 day data collection period. In week 13 the researcher will call them again and ask them to wear the device again (for 7 days) during week 13.

We will collect data for Quality of life using the 26-item validated WHOQOL-BREF at weeks 0 and 13.⁸³ Physical Function will be measured using the 20-item NIH PROMIS Physical Function measure. Participation will be measured using the 8-item NIH PROMIS Ability to Participate in Social Roles and Satisfaction with Participation in Social Roles measures. With the exception of the NCI ASA, copies of all measures are included in the appendices.

Clinical Measures: We will collect data for MetS component factors by assessing changes from baseline to week 13 in Systolic blood pressure, Weight, Hemoglobin A1c (HbA1c), and Triglyceride and HDL levels. Anthropometry and biomarker measures will be collected in the clinic following established anthropometry guidelines.⁸⁴

Symptom burden: We will collect data for symptom burden in a subsample of participants using and Ecological Momentary Assessment (EMA) called Movisens XS. A subsample of participants will be asked to download the Movisens application on their phone via a QR code texted to the participant (Android phones only). The application will prompt participants twice per day (12 pm and 8pm) to answer questions about daily symptoms (e.g., fatigue or pain) on the phone. The severity of 13 common cancer-related symptoms (EMA appendix) during the previous two hours will be assessed on a 0–10 numerical rating scale, with 0 being “not present” and 10 being “as bad as you can imagine.” Participants will also be asked to rate the quality of their sleep (first thing in the morning only) and to describe, using free text, what they are doing at the time of the EMA prompt (e.g., washing dishes, watching TV). Participants will be asked to complete the symptom reporting throughout the intervention (12 weeks). It will take about 30-50 seconds to complete each report.

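### Section 4.0 lists weight instead of waist among the MetS components followed to week 13, and the automaticity item has two conflicting schedules

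*Combined protocol and SAP*

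**What the plan says.** **MetS.** Section 2.0 says the syndrome "includes having three of the following five criteria: (a) a large waistline", followed by blood pressure, HbA1c, triglycerides and HDL. The inclusion criteria in Section 3.0 repeat this: "Three of the following 5 criteria must be present for MetS: a large waistline", followed by the same four. For follow-up, Section 4.0 (Clinical Measures) gives the list as "MetS component factors by assessing changes from baseline to week 13 in Systolic blood pressure, Weight, Hemoglobin A1c (HbA1c), and Triglyceride and HDL levels". The next sentence there says that anthropometry and biomarkers are collected in the clinic, without naming any anthropometric measure.

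**Where waist is named as a measurement.** On the clinic route: "Once consented, the RA will measure the participant's waist". On the survivorship-cohort route, initial selection is by self-report of "two of the following four criteria: high cholesterol, hypertension, diabetes, and a BMI" at or above 25. Then "Data collection, including a blood draw to confirm MetS status will occur" in the participant's home. Of the later baseline visit the plan says "The first visit be in person and will consist of the participant completing psychosocial measures, a 24 hour dietary recall", plus instruction on optional devices. Waist appears in none of these cohort-route steps, nor in the description of the week-13 visit. Section 3.0 also says that "we will use a modified classification criteria, based on recruitment source".

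**Automaticity.** Section 3.0 (Experimental Design and Methods) has the single text-message item completed two weeks apart, with the bracket week 0-2. Section 4.0 (Behavioral Measures) has it given every two weeks, for habits the participant has chosen. The lead-in to Data Collection Feasibility places the primary and secondary measures at baseline and week 13.

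**Why these measures count.** Aim 1 names habit development as the primary behavioral measure and MetS as the primary clinical measure. Feasibility of collecting them is judged by mean percent missing, per instrument and for the whole battery.

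**The concern.** A pilot of this kind exists largely to show whether the full trial's primary measures can be collected. Missingness can be counted only against a list of what was meant to be collected. If waist is not on the list, a waist that is never taken does not register as missing, and the clinical measures can be reported as complete with four of the five MetS components in hand. The full trial would then lack evidence on whether the fifth can be obtained at follow-up, or in the home on the cohort route.

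The automaticity item has a related problem. Percent missing is 1 minus (ratings received / ratings expected), and the number expected depends on the schedule. Two sections give different schedules, and the baseline time point in the general lead-in cannot apply to a habit that has not yet been chosen.

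**Working it through.** The plan states no figure for either part, so the check is mainly a comparison of the sections.

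**1. Definition against follow-up list.**

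| Item | MetS criterion (Sections 2.0, 3.0) | On the Section 4.0 list |
|---|---|---|
| Waist | yes | no |
| Blood pressure | yes | yes (systolic) |
| HbA1c | yes | yes |
| Triglycerides | yes | yes |
| HDL | yes | yes |
| Weight | no | yes |

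Four of five criteria are listed. Waist is absent, and weight is listed without being a criterion.

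**2. Route and time.** A waist measurement is stated for clinic recruits at entry. It is not stated for clinic recruits at week 13, or for cohort recruits at baseline or week 13. The anthropometry sentence places collection in the clinic, whereas baseline collection on the cohort route is in the home, so that sentence does not clearly reach cohort recruits at baseline.

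**3. What is lost without waist at week 13.** Take the other four criteria as known, each met or not: 2^4 = 16 patterns.
- None or one met: C(4,0) + C(4,1) = 1 + 4 = 5. Not MetS, whatever the waist.
- Three or four met: C(4,3) + C(4,4) = 4 + 1 = 5. MetS, whatever the waist.
- Exactly two met: C(4,2) = 6. Status depends on waist.

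Check: 5 + 5 + 6 = 16. From the other side, the patterns of five criteria with at least three met number C(5,3) + C(5,4) + C(5,5) = 10 + 5 + 1 = 16, and 6 of these qualify only because of waist. These are counts of logical patterns. The documents give no component frequencies, so they do not translate into a share of participants.

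**4. Automaticity time points, in weeks.**
- Section 3.0, literal reading: {0, 2}.
- Section 4.0, two-weekly: {2, 4, 6, 8, 10, 12}, or the same with 0 added. The next occasion would be week 14.
- General lead-in in Section 4.0: {0, 13}.

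The first two both describe tracking during the intervention, and they differ. Week 13 is in neither.

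**5. Which habits can have a baseline rating.** Habits are identified in the sessions of weeks 2, 4, 6, 8 and 10, two each time: 5 x 2 = 10, which agrees with the ten per person in the Habit Development Intervention text. Section 3.0 puts the first intervention visit two weeks after baseline collection is complete. Every self-selected habit is therefore chosen after the baseline visit, and none can have a rating from it.

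**The case against.** **Waist may be taken anyway.** Anthropometry is to be collected in the clinic under established guidelines, and Section 3.0 promises a consistent set of measures at a clinic-based week-13 visit. A reader might infer from the Section 4.0 list that waist has been dropped from follow-up. The documents do not support that: nothing excludes it. What stands is narrower. Weight by itself satisfies the word anthropometry, the consistent set is not itemized, and the source-dependent classification concerns entry rather than follow-up. The plan leaves waist possible but unsecured.

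**Section 4.0 speaks of component factors, not of three-of-five status at week 13.** That is true, and analysis is descriptive with no inference planned, so no stated endpoint becomes incalculable. The omission still leaves out one component of what Aim 1 calls a primary clinical measure.

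**The automaticity statements may be compatible.** A reader might infer three mutually contradictory schedules. That goes too far. Two-weekly tracking during treatment can coexist with a baseline and week-13 battery, so a two-weekly series that misses week 13 is a gap in wording. The bracket week 0-2 may also be a typing slip, which the documents do not settle. One plain conflict remains, between Sections 3.0 and 4.0 on in-treatment tracking, together with a baseline time point that cannot apply to habits not yet chosen. Taking the first rating when a habit is selected is a natural reading, but it is not stated.

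**Conclusion.** The point holds as a gap in the measurement plan that should be closed. The follow-up list covers four of the five MetS components. Waist is secured only at entry on the clinic route. If it is not taken at week 13, three-of-five status is undetermined whenever exactly two of the other four criteria are met. For automaticity, the primary habit-development measure has no workable baseline and week-13 denominator as written.

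A reader might infer that the feasibility decision itself is compromised. It is not, as written. Waist is not on the list and so does not enter the criterion. The stated limits allow up to 97% missing for an instrument and 95% for the battery, so the automaticity item would have to be almost wholly missing, on whatever denominator is used, to fail its own limit. The harm is to what the pilot can report for planning the full trial.

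The conclusion assumes that staff follow the Section 4.0 list as written. If waist is already taken on both routes at both times, the waist point reduces to naming it and counting it. The size of any data loss cannot be computed, because the documents give neither the split between recruitment routes nor the component frequencies.

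**What to change.** In Section 4.0 (Clinical Measures), add waist circumference at baseline and week 13 for both recruitment routes. Say where it is taken at baseline on the cohort route, keep weight as an additional measure, and count waist in the missingness battery. The cost is a tape measurement at in-person visits already planned: at most 48 at week 13 (fewer with dropout), plus one at baseline for each cohort-route participant.

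Reconcile Section 3.0 (Experimental Design and Methods) and Section 4.0 (Behavioral Measures) to one automaticity schedule. Take each habit's first rating when the habit is selected, state which habits are rated on each later occasion and whether there is a week-13 rating, and define percent missing on that schedule. No particular number of ratings is needed. This is a change of wording only, unless a week-13 rating is added, which would mean one further text-message contact.
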